6.8. Power Calculations and Analyses

Power calculations were performed for the primary aim of evaluating the effect of the intervention on the parent-level recognition of AD symptoms post-test and at three months post intervention. The outcome was treated as both continuous and binary for the most conservative test of meaningful change.

6.8.1. Design Features: The design is a cluster randomized trial with random assignment of 10 schools to each of two arms. Subjects will be nested within schools and classrooms. We posit a relatively lower intracluster correlation coefficient (ICC) for schools than for classrooms. Estimates have been adjusted for unreliability of the outcome (estimated at R=0.70) and clustering. The variance inflation factor (V_{if}) =1.87, assuming that n_e (the average number of subjects within a class) =20; the intracluster correlation coefficient for class (ICC_{class}) =0.03 and for school (ICC_{school})=0.015; N_s (5th and 6th grade classes) =2. The pooled σ (standard deviation) is estimated at 1.06, based on our prior work. Assuming a two-tailed test with σ =0.05, power (1- β =80%), n=400 parents per group will be adequate to detect posited effect sizes shown below.

6.8.2.Power and Analyses for 3 Level Cluster Sampling and Evaluation of Pre- and Post-Intervention, Treating AD Symptom Recognition as Continuous: Power calculations were from the perspective of least detectable group differences in rates of change (slopes), adjusted for the design effects of correlations induced by repeated measures of subjects nested within classrooms and schools. Different scenarios regarding correlations among the repeated outcomes were considered. The mixed model for rate of change in outcome: $y_{ijk} = \beta_0 + \beta_k T_{ij} + FU_{lm}$, (equation 1) where ijk refers to subjects, time points and group; FU_{lm} is the random effect associated with school and class; T=0 is the pre-test and immediate post-test and T=1 is the 3 month post-test. The sample size formula for the rate of change⁵⁵ is: $m = \frac{2(z_\alpha + z_\beta)^2 \sigma^2 (1-\rho)}{ns_\alpha^2 d^2}$, with m=m*V_{if}/R;⁵⁶

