 $s_{x}^{2} = \sum (t_{j} - \bar{t}) = 0.667 \ V_{if} = (1 + (n_{e} - 1)\rho_{e})(1 + (n_{s} - 1)\rho_{s}n_{e}\rho_{e}/(1 + (n_{e} - 1)\rho_{e})) \ , \ \text{where} \ n_{e} \ \text{is the number of subjects}$ within class, n_s is the number of classes within schools, rho e is the ICC for classes, rho s is the ICC for school.⁵⁷ For different values of p_{rm} (the average correlation of the repeated outcome measures, we provide detectable rates of change and accompanying Cohen's d effect sizes. For ρ_m=0.4, the detectable rate of change (β₁=0.29) over 3 months from the model in equation (1) translates to a Cohen's d (endpoint difference between the intervention and control group/pooled standard deviation) of 0.27 or for ρ_m=0.6, β₁=0.27 and Cohen's d=0.25. Given the above scenarios, we will be able to detect relatively small effect sizes in terms of endpoint differences between the intervention and control groups. The Ancova model using a pretest score as covariate will improve power. The formula is $y_{iik} = y_{i0k} + \beta_0 + \beta_{ik} + FU_{lm}$ where y_{i0k} is pretest score for subject i in group k and j is the time point (j=1 for immediate post-test and j=2 for the 3 month post-test). Assuming the intervention group improves by δ (Cohen's d= δ/σ) over the control group at the 3 month post-test, we can use different weights for the immediate post-test in calculating power (a₁=0 indicates no increased test performance for the intervention as contrasted with the control group at immediate post-test, a₁=1/2 indicates 50% increased performance of the intervention over the control group, and a₁=1 indicates 100% increased performance of the intervention as contrasted with the control group). The sample size formula for the Ancova model⁵⁸ is: $m = \frac{2(z_a + z_\beta)^2 \sigma^2 (1 - r_b^2)}{2 \sigma^2 (1 - r_b^2)}$ with m=m*V_{if}/R, $r_b^2 = \sum (a_i r_{ij}) / \sqrt{\sum \sum a_i a_j r_{ij}}$, $\Delta = \sum (a_i d_j) / \sum \sum (a_i a_j r_{ij})$. As shown in **Table**

2, smaller effect sizes are detectable under the scenario that there is some improvement immediately as well as at 3 months.

Table 2. Power Analyses for Ancova.									
Correlation	a ₁ =0	a ₁ =1/2	a ₁ =1						
ρ=0.4	δ=0.315 (d=0.300)	δ=0.210 (d=0.200)	δ=0.158 (d=0.149)						
ρ=0.5	δ=0.298 (d=0.281)	δ=0.199 (d=0.188)	δ=0.149 (d=0.141)						
ρ=0.6	δ=0.275 (d=0.259)	δ=0.184 (d=0.174)	δ=0.138 (d=0.130)						
ρ=0.7	δ=0.246 (d=0.232)	δ=0.164 (d=0.154)	δ=0.123 (d=0.116)						

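### Section 6.8.2 says ANCOVA will improve power, but against the slope model with no early effect this holds only for correlations below 0.5, and the printed slope figure at 0.4 does not follow from the plan's formula

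*Combined protocol and SAP*

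**What the plan says.** Section 6.8.1 sets inputs that serve both continuous-outcome models: "Assuming a two-tailed test with σ =0.05, power (1- β =80%), n=400 parents per group will be adequate" (the σ there evidently stands for alpha); "The pooled σ (standard deviation) is estimated at 1.06, based on our prior work"; "The variance inflation factor (V_{if}) =1.87"; and "Estimates have been adjusted for unreliability of the outcome (estimated at R=0.70) and clustering".

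Section 6.8.2 first presents a slope model with the time coding "T=0 is the pre-test and immediate post-test and T=1 is the 3 month post-test". Its detectable slopes are 0.29 (d=0.27) at a correlation of 0.4 and 0.27 (d=0.25) at 0.6; the second is printed as "of 0.27 or for ρ_m=0.6, β₁=0.27".

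The section then turns to ANCOVA: "The Ancova model using a pretest score as covariate will improve power". Table 2 gives the ANCOVA detectable differences for correlations 0.4 to 0.7 under three weights for the immediate post-test. In the a1=0 column (no early group difference) the entry at 0.4 begins "δ=0.315 (d=0.300", and the entry at 0.6 is 0.275 (d=0.259). The text introducing Table 2 links the smaller values under a1=1/2 and a1=1 to improvement that is already present at the immediate post-test.

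**The concern.** The ANCOVA sentence comes almost directly after the slope results, and the slope model is the only earlier continuous-outcome model in 6.8.2. A reader will take it as the comparator. The like-for-like column is a1=0, because the slope coding 0, 0, 1 equates the slope with the 3-month difference only if the groups do not differ at the immediate post-test. In that column the printed ANCOVA effects exceed the printed slope effects at both correlations the two models share: 0.315 against 0.29, and 0.275 against 0.27. A larger detectable effect means less power, so the plan's own numbers appear to contradict its statement.

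Two things are at stake. One is a stated property of the analysis that the formulas do not deliver over part of the tabulated range. The other is a stated detectable effect that 400 per group may not reach with 80% power.

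**Working it through.** **Inputs (6.8.1 and 6.8.2).** 400 per group, two-sided alpha 0.05 (z = 1.96), power 80% (z = 0.8416), SD 1.06, variance inflation factor 1.87, reliability 0.70, sum of squares of the time codes 0.667 (codes 0, 0, 1 give 2/3).

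**Common multiplier.** K = sqrt[2 × (1.96 + 0.8416)² × 1.06² × (1.87/0.70) / 400] = sqrt(47.12/400) = 0.3432.

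**Formulas.**
- Slope: detectable difference = K × sqrt[(1−ρ)/0.667] = K × sqrt[1.5(1−ρ)].
- ANCOVA, a1=0: detectable difference = K × sqrt(1−ρ²).

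**Reproducing the plan.** The ANCOVA formula gives 0.315, 0.297, 0.275 and 0.245 at ρ = 0.4, 0.5, 0.6 and 0.7. Table 2 prints 0.315, 0.298, 0.275 and 0.246. Solving back from the printed values gives 399, 398, 399 and 397 per group, so this column reproduces. (At 0.4, 0.315/1.06 = 0.297; the printed d of 0.300 is slightly high.) The slope formula at ρ = 0.6 gives 0.266 (d=0.251), which agrees with the printed 0.27 (d=0.25) after rounding.

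**The slope figure at 0.4 does not reproduce.** The formula gives 0.3432 × sqrt(0.9) = 0.326, d = 0.307. The plan prints 0.29 and 0.27.
- Power at a difference of 0.29: Φ(2.8016 × 0.29/0.3256 − 1.96) = Φ(0.535), about 70%.
- Sample size for 80% power at 0.29: 400 × (0.3256/0.29)², about 504 per group.
- The two printed slopes also disagree with each other. Under the formula their ratio must be sqrt(0.6/0.4) = 1.225 whatever the SD, inflation factor, reliability, sample size or denominator. The printed ratio is 0.29/0.27 = 1.074, and rounding can raise it to at most 0.295/0.265 = 1.113.
- A one-sided alpha gives 0.289 at 0.4 but 0.236 at 0.6, so it does not explain the pair.

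**Comparison of the two models.** K cancels. ANCOVA has the smaller variance factor when 1−ρ² < 1.5(1−ρ), that is 1+ρ < 1.5, so ρ < 0.5. The ratio of required sample sizes, ANCOVA to slope, is (1+ρ)/1.5. The last column below is the ANCOVA power at the difference the slope model detects with 80% power: Φ(2.8016 × sqrt[1.5/(1+ρ)] − 1.96).

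| ρ | 1.5(1−ρ) | 1−ρ² | Slope difference (d) | ANCOVA a1=0 difference (d) | N ratio | ANCOVA power |
|---|---|---|---|---|---|---|
| 0.4 | 0.90 | 0.84 | 0.326 (0.307) | 0.315 (0.297) | 0.93 | 82.6% |
| 0.5 | 0.75 | 0.75 | 0.297 (0.280) | 0.297 (0.280) | 1.00 | 80.0% |
| 0.6 | 0.60 | 0.64 | 0.266 (0.251) | 0.275 (0.259) | 1.07 | 77.4% |
| 0.7 | 0.45 | 0.51 | 0.230 (0.217) | 0.245 (0.231) | 1.13 | 74.9% |

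**The other columns of Table 2.** The a1=1/2 and a1=1 entries equal the a1=0 entries divided by 1.5 and 2, to rounding: 0.315/1.5 = 0.210 and 0.315/2 = 0.158. That reduction comes from the assumed early effect. No slope figures are given for those scenarios, so they do not show what the covariate adds.

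**The case against.** **The comparator is not named.** The sentence could mean a gain over a post-test analysis without the covariate. On that reading it is true at every positive correlation, since 1−ρ² < 1. This stands as a limit on the finding: the slope model as comparator is inferred from position. But 6.8.2 presents no unadjusted post-test model, so the text offers no other comparator.

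**Two of Table 2's three columns favour ANCOVA.** All eight a1=1/2 and a1=1 entries lie below both printed slope figures, and the plan says that they assume some immediate improvement. That is fair, and the point must be confined to a1=0. Those columns still do not support the sentence, which credits the pre-test covariate and not an added early effect.

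**The crossover depends on how the formulas are read.** The slope denominator is printed as n times s². Taking that product as 0.667 reproduces the slope figure at 0.6. Read literally as 3 × 0.667 = 2, it gives 0.188 and 0.153, which match nothing printed, and ANCOVA would then gain at no positive correlation. The ANCOVA denominator is not legible in the available text; 1−ρ² for a1=0 rests on its fit to Table 2. Both readings are therefore supported by the plan's own figures but remain assumptions.

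**A stronger reading is tempting.** From the printed numbers a reader might infer that ANCOVA is the weaker analysis at both shared correlations. The documents do not support that at 0.4. With the slope figure recomputed, ANCOVA is slightly better there (0.315 against 0.326), as the plan says; the printed reversal is a by-product of the faulty 0.29.

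**Conclusion.** The sentence is wrong as an unqualified statement against the slope model. For a1=0, ANCOVA gains about 2.6 points of power at a correlation of 0.4, ties at 0.5, and loses about 2.6 and 5 points at 0.6 and 0.7. Separately, the slope effect printed for 0.4 is too small by the plan's own formula: 0.326 (d=0.307) is what 400 per group detects with 80% power, and 0.29 has about 70%.

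The comparison rests on the slope model as comparator, on a1=0, on a slope denominator of 0.667 and on an ANCOVA factor of 1−ρ². It does not depend on the SD, inflation factor, reliability or sample size, which both models share.

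A reader might also infer that ANCOVA is a poor choice, or that the trial needs more parents. Neither follows. The power differences are small, the plan does not say that it chooses its model on this sentence, and Table 2's a1=0 column is consistent with 400 per group. This is a minor correction to the stated power.

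**What to change.** In 6.8.2:

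1. Restate the slope result at a correlation of 0.4 as 0.326 (d=0.307), or show how 0.29 (d=0.27) was obtained.
2. Limit the ANCOVA sentence, for example: With no group difference at the immediate post-test (a1=0), ANCOVA has more power than the slope model when the correlation is below 0.5, equal power at 0.5, and about 2.6 and 5 points less at 0.6 and 0.7.
3. Print the detectable d for both models side by side for a1=0, at correlations 0.4, 0.5, 0.6 and 0.7: slope 0.307, 0.280, 0.251, 0.217; ANCOVA 0.297, 0.280, 0.259, 0.231.
4. State that the smaller effects under a1=1/2 and a1=1 come from the assumed early effect, not from the covariate.

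The cost is some wording and one short table. The sample size and the analyses are unchanged. The sponsor has to accept a less favourable stated detectable effect at 0.4 and a narrower claim for ANCOVA.

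### Section 6.8.2 states detectable effects that its own formulas do not give: the a₁=1/2 and a₁=1 columns of Table 2, and the slope at a correlation of 0.4

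*Combined protocol and SAP*

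**What the plan says.** Section 6.8 powers the trial on parent-level recognition of symptoms, which it calls the primary aim. Section 6.8.1 sets a two-tailed 5% test ("Assuming a two-tailed test with σ =0.05", where σ evidently stands for α), 80% power, a reliability of 0.70 and a variance inflation factor of 1.87. It adds that "The pooled σ (standard deviation) is estimated at 1.06" and that "n=400 parents per group will be adequate to detect posited effect sizes shown below".

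Section 6.8.2 then gives two sets of detectable effects.

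- **Slope model:** "the detectable rate of change (β₁=0.29) over 3 months", with d=0.27, at a correlation of 0.4; "or for ρ_m=0.6, β₁=0.27", with d=0.25.
- **Ancova model (Table 2):** differences for correlations 0.4 to 0.7 and three weights for the immediate post-test. At 0.4 they are 0.315 (a₁=0), 0.210 (a₁=1/2) and, for a₁=1, "δ=0.158 (d=0.149".

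From Table 2 the plan concludes that "smaller effect sizes are detectable under the scenario that there is some improvement immediately as well as at 3 months".

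**The concern.** Two patterns in the printed figures are suspicious before any recalculation.

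First, in every row of Table 2 the second and third columns are the first divided by 1.5 and by 2. Halving a detectable effect requires a fourfold fall in variance. Adding one further post-test cannot give that.

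Second, the slope formula makes the detectable slope proportional to √(1−ρ), so the values at 0.4 and 0.6 must differ by √(0.6/0.4) = 1.22. The printed ratio is 0.29/0.27 = 1.07. Rounding cannot close the gap: 0.295/0.265 is only 1.11.

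These are the plan's sensitivity figures for its primary parent outcome. A reader would take effects of d=0.12 to 0.20 as detectable with 80% power if there is early improvement, and could read a null result as excluding effects that small.

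**Working it through.** **Inputs (section 6.8.1).** n=400 per arm, σ=1.06, inflation factor 1.87 (taken as stated), R=0.70, z sum = 1.960+0.842 = 2.802. Since the plan multiplies m by 1.87/0.70, the effective m is 400×0.70/1.87 = 149.7 per arm.

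**Slope.** β = √[2 × 2.802² × 1.06² × (1−ρ) / (0.667 × 149.7)].

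- ρ=0.6: 0.266, d=0.25. This reproduces the plan.
- ρ=0.4: 0.326, d=0.31. The plan prints 0.29 and 0.27.

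Power at a slope of 0.29 is Φ(2.802×0.29/0.3255 − 1.960) = Φ(0.54), about 70%. For 80% power the plan would need 400×(0.3255/0.29)² ≈ 504 per arm. A one-sided 5% test gives 0.289 at ρ=0.4, but it contradicts the stated two-tailed test and gives 0.236 at ρ=0.6. No single setting tried gives both printed slopes.

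**Ancova, a₁=0.** δ = √[2 × 2.802² × 1.06² × (1−ρ²) / 149.7] gives 0.315, 0.297, 0.275, 0.245. The plan prints 0.315, 0.298, 0.275, 0.246. With m cut to 149 all four agree to three decimals, so the inputs are the plan's own.

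**How the other columns arose.** With m=149, dividing the a₁=0 values by 1.5 gives 0.2102, 0.1986, 0.1835, 0.1638, and by 2 gives 0.1577, 0.1490, 0.1376, 0.1229. These match all eight printed differences. The numerator of Δ was used without its denominator, and r_b was held at ρ.

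**Ancova with the denominator.** Take weights (a₁, 1) and the same ρ between all pairs of visits.

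- S = a₁² + 1 + 2a₁ρ
- r_b² = [(1+a₁)ρ]²/S
- D = Σa_j d_j/(δ√S): (1+a₁)/√S if the early effect equals δ, or (1+a₁²)/√S if it equals a₁δ
- δ = √[2 × 2.802² × 1.06² × (1−r_b²)/149.7]/D

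For a₁=1, ρ=0.4: S=2.8, r_b²=0.64/2.8=0.229, the root is 0.301, D=2/√2.8=1.195, and δ=0.301/1.195=0.252. Power at the printed 0.158 is Φ(2.802×0.158/0.252 − 1.960) ≈ 42%.

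| ρ | a₁=1 printed | a₁=1 recalculated | power at printed | a₁=1/2 printed | recalculated, early effect δ/2 | recalculated, early effect δ |
|---|---|---|---|---|---|---|
| 0.4 | 0.158 | 0.252 | 42% | 0.210 | 0.312 | 0.260 |
| 0.5 | 0.149 | 0.243 | 41% | 0.199 | 0.299 | 0.249 |
| 0.6 | 0.138 | 0.228 | 40% | 0.184 | 0.280 | 0.233 |
| 0.7 | 0.123 | 0.206 | 39% | 0.164 | 0.253 | 0.211 |

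At the printed a₁=1/2 values, power is 44% to 47% with a half-size early effect and 59% to 62% with a full one. Reaching 80% at the printed a₁=1 values would need about 1,020 to 1,120 parents per arm.

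**A check without the formula.** Two post-tests that are not negatively correlated after adjustment for the pre-test can at most halve the variance. If the early effect is no larger than the later one, the detectable difference cannot fall below the a₁=0 value divided by √2: 0.223, 0.211, 0.194, 0.174. All eight printed cells lie below this floor.

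**The case against.** The strongest objection is that the Ancova formula is damaged in the available text: the denominator of the sample-size fraction is lost, and squares and roots are uncertain. The recalculation is therefore partly a reconstruction. That is fair, so variants were tried: r_b squared, r_b² literally as printed, or r_b fixed at ρ, and Δ with or without a square root. At a₁=1 and ρ=0.4, those that keep the denominator run from 0.207 to 0.44; none gives 0.158. The low end takes r_b² as printed, which also breaks the plan's own a₁=0 column (0.217 instead of 0.275 at ρ=0.6). The √2 floor does not depend on the formula at all.

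The slope formula also prints a factor n beside the sum of squares. Applied literally with n=3 it gives 0.188 and 0.153, and neither printed slope appears. Leaving it out is reasonable because 0.667 is already a sum over the three time points. The 1.22 ratio holds either way.

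Other points stand as limits. Most of what a cautious reader would rely on is intact: the a₁=0 column, the slope at 0.6 and the binary power in Table 3 are not touched. The plan does not name d=0.12 to 0.15 as a design target. Its conclusion about early improvement keeps its direction for a₁=1 (0.252 against 0.315). The plan's remark that 0.4 is conservative belongs to the binary analysis in section 6.8.3, not to 6.8.2. And a₁=1/2 can be read in two ways, so its correction is a range.

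**Conclusion.** The concern holds. Eight of the twelve differences in Table 2 and one of the two slopes do not follow from the stated inputs and formulas, and all nine err on the favourable side.

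- **a₁=1:** the detectable difference is 60% to 67% larger than printed (d=0.19 to 0.24, not 0.12 to 0.15).
- **a₁=1/2:** it is 24% to 28% larger with a full early effect and 49% to 54% larger with a half-size one. In the latter case there is essentially no gain over a₁=0: slightly smaller at ρ=0.4, slightly larger from 0.5 upwards.
- **Slope at ρ=0.4:** 0.33 rather than 0.29.

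The recalculated Ancova values assume that the correlation between the two post-tests equals that of each with the pre-test, and that Δ is standardised by the square root of the double sum. The division by 1.5 and 2, the √2 floor and the slope ratio do not need the second assumption.

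**What to change.** Recalculate the a₁=1/2 and a₁=1 columns with Δ = Σa_j d_j/√(ΣΣa_i a_j r_ij) and the matching r_b, and state the correlation assumed between the post-tests. Say whether a₁=1/2 means a weight with a full early effect or a half-size early effect, and tabulate that case. Restate the slope at a correlation of 0.4 as 0.33 (d=0.31).

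Reword the conclusion drawn from Table 2: a full early effect lowers the detectable difference moderately, and a half-size one hardly at all. Do not present d of 0.12 to 0.20 from those two columns as detectable with 80% power.

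Two small repairs can go with it: print α for the 0.05 level, and correct the first-row values d=0.300 and 0.200, since 0.315/1.06=0.297 and 0.210/1.06=0.198 (the second falls away once its column is replaced).

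The cost is a short recalculation and less favourable figures. Sample size, enrolment and the analysis models are unchanged.

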control group at immediate post-test. The table below assumes fixed adjusted differences of 16.7%. (The 3 month post-test difference adjusted by the immediate post-test (P_{22} - P_{21} -(P_{12} - P_{11})=16.7%.) This restriction permits comparison of the power across different models. The models show either 5% improvement in rates of passing at 3 month post-test in the control group and or 5% or no improvement at the immediate post-test in the intervention group. **Table 3** shows that for different pre-test passing rates (from 30% to 50%), the posited adjusted difference of 16.7% can be detected with > 80% power when the correlation between repeated measure ρ =0.4 (which is conservative considering that the 3 repeated measures are within 3 months, and that increasing ρ will increase power). It also shows that as the average passing rate at 3 months approaches 50%, power will be the lowest in comparison with lower or higher passing rates. If we only used two waves of data (pretest and 3 month), the minimal detectable difference in passing rates between the intervention and control groups at 3 month post-test would be18%. Dropping the immediate post-test will result in a slight loss in power.

Table 3. Power Analyses for AD recognition										
Model	Pre-	Pre- Immediate		3 month		Adjusted	Power			
	Test	Post-test		Post-test		difference				
	P ₀	P ₁₁	P ₁₂	P ₂₁	P ₂₂	P ₂₂ -P ₂₁ -(P ₁₂ -P ₁₁)	ρ=0.4	ρ=0.5		
No improvement in	30%	30%	30%	30%	46.7%	16.7%	85.37%	89.51%		
control	40%	40%	40%	40%	56.7%	16.7%	83.05%	86.54%		
Immediate post test	50%	50%	50%	50%	66.7%	16.7%	83.45%	85.87%		
Improvement in	30%	30%	35%	30%	51.7%	16.7%	83.33%	87.27%		
intervention	40%	40%	45%	40%	61.7%	16.7%	82.71%	85.69%		
Immediate post test	50%	50%	55%	50%	71.7%	16.7%	84.81%	86.67%		
Improvement in	30%	30%	35%	35%	56.7%	16.7%	80.00%	84.02%		
intervention and	40%	40%	45%	45%	66.7%	16.7%	82.93%	85.62%		
control post test	50%	50%	55%	55%	76.7%	16.7%	87.82%	89.27%		

Passing rate: P_{jk} (y=1): j is the time point (j=0 for pre-test, j=1 for immediate post-test and j=2 for 3 month post-test. K=1 for control, k=2 for intervention)

6.8.4. Secondary Aims

Analyses of Correlates and Predictors of AD Recognition: Treating the outcome as continuous, relationships with variables such as economic need, educational attainment and other demographic variables will be examined using a mixed model similar to that described above for continuous outcomes.

Measurement Analyses: The proposed Data Coordinating Center (DCC) has considerable experience in the conduct of measurement analyses. A detailed explication is beyond the scope of this proposal. Briefly, qualitative methods will be used to develop an item pool for future analyses and development of an ancillary outcome measure. Although extensive qualitative work informed the development of the proposed legacy outcome measure used to power this study; it is recognized that additional measurement work would be a valuable contribution of this project. Given the large sample sizes, it would be possible to begin the development of additional measures of AD recognition. Development of the measure using factor analytic and item response theory models is beyond the scope of this project; however, generation of the item pool will be an invaluable first step in this process. The qualitative methods will include (1) convening experts and focus groups to generate additional items for the item pool; (2) ratings of the importance of the items and relationship to the construct: (3) cognitive interviews to determine the meaning of the items; (4) translation of the items. **6.8.5. Missing Data:** Analyses will follow the intent-to-treat principle. Based on previous experience with similar programs, we anticipate minimal missing data. Using the above-described FIML approach to estimate treatment effects, assuming that missing data are either missing completely at random or at random; this method, with a covariate to adjust for attrition bias, yields intent-to-treat parameter estimates that are consistent with that expected if there were no missing data. Scales will be prorated for missing data, using individual imputation algorithms. If substantial missing outcome data are observed, we will use a specific imputation approach, e.g., Markov Chain Monte Carlo procedures⁶⁰ based on the amount and pattern of missing data. In the event of substantial missing data, SAS Proc MI will be used in sensitivity analyses. We will perform joint simultaneous imputation; at least 50 multiple imputations will be generated and PROC MIAnalyze will be used to combine the results and estimate the log-odds, adjusted standard errors and significance. If substantial imbalance is observed, we will use propensity score analyses to equate the groups.

6.8.7. Data Management: The Research Division of the Hebrew Home at Riverdale will serve as the DCC, and will perform data monitoring and quality assurance checks of the data, including periodic review of data distributions. Statistical staff will convert data files to SPSS or SAS in order to facilitate performance of analyses. (See subcontract budget justification for further details).

6.9 Timeline. We plan for a 6-month startup period, entering the first school in Month 7 of Y1, and thereafter in new schools, approximately every 1-2months during the 6-7month accessible school year (eliminating vacation and summative test periods; parental assessments can occur year-long). Data collection for all but follow-up reports of events will cease in Month 3 of Year 5, allowing a 9-month period for data analysis, preparation of results, and completion of recruitment measures. Throughout the timeline, schools receiving the intervention arm and having completed all study components will receive the active control condition, as requested by our partnering schools given NYC mandates to general health education initiatives. **Table 4** shows the timeline.

Table 4. School Enrollment Timeline														
Year	Visit	Month												
		1	2	3	4	5	6	7	8	9	10	11	12	
1	Start	Item pool generation Start-up period; recruitment;									S2			
	1-wk	cartoon creation (As described in 6.5.1.a-c.)						S1			S2			
	3-m										S1			
2	Start		S3	S4			S5	S6			S7	S8		
	1-wk		S3	S4			S5	S6			S7	S8		
	3-m	S2				S3	S4			S5	S6			
3	Start		S9	S10			S11	S12			S13	S14		
	1-wk		S9	S10			S11	S12			S13	S14		
	3-m	S7	S8			S11	S12			S11	S12			
4	Start		S15	S16			S17	S18			S19	S20		
	1-wk		S15	S16			S17	S18			S19	S20		
	3-m	S13	S14			S15	S16			S17	S18			
5	Start													
	1-wk				Data	Data analysis, manuscript preparation; final data collection if necessary								
	3-m	S19	S20											

REFERENCES:

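### The multiple-imputation sensitivity analysis (Section 6.8.5) has no school or class term; run as written, it would understate the combined standard errors

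*Combined protocol and SAP*

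**What the plan says.** Section 6.8.5 bases the treatment effect on full-information likelihood: "Using the above-described FIML approach to estimate treatment effects, assuming that missing data are either missing completely at random or at random". It gives no missing fraction and says only "we anticipate minimal missing data".

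If many outcomes are missing, "we will use a specific imputation approach, e.g., Markov Chain Monte Carlo procedures", with the choice depending on how much is missing and in what pattern. The role of the software is then limited: "In the event of substantial missing data, SAS Proc MI will be used in sensitivity analyses". The imputation is to be joint, and "at least 50 multiple imputations will be generated and PROC MIAnalyze will be used to combine the results", as log-odds with their standard errors. No imputation variables are listed, and neither school nor class is mentioned.

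On the design, Section 6.8.1 says "Subjects will be nested within schools and classrooms". The models in Sections 6.8.2 and 6.8.3 include a random term for school and class, and the sample size rests on a variance inflation factor of 1.87.

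**The concern.** The MCMC method of PROC MI, which the plan gives as its example, fits one multivariate normal model to rows treated as independent. It has no random-effects term. If nothing is added for clustering, a missing parent outcome is drawn without the deviation shared by that parent's school and class. Each completed data set then shows less within-school correlation than the trial really has, and Rubin's rules do not restore it. More imputations do not help.

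The imputation model would thus be simpler than the analysis model in the feature that defines a cluster trial. The analysis is triggered only when missing data are substantial, which is when the shortfall is largest. Its purpose is to check the FIML result. With standard errors that are too small, it could appear to confirm or sharpen a borderline result for a reason unrelated to the missing data.

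**Working it through.** **Inputs from Section 6.8.1.** 10 schools per arm; 2 classes per school; 20 subjects per class; ICC 0.03 for class and 0.015 for school; 400 parents per arm; SD 1.06; reliability 0.70. From Table 2: detectable difference 0.315 at correlation 0.4.

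**Assumed.** Missing fraction f of 5% to 30%, missing completely at random in the closed form. School and class variance components of 0.015 each and residual 0.97, so that parents correlate 0.03 within a class and 0.015 between classes of one school.

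**1. The plan's own figures.**
- VIF = (1 + 19 × 0.03) × (1 + 0.015 × 20 / 1.57) = 1.57 + 0.30 = 1.87, as stated. The formula as it reads in Section 6.8.2 has a further class-ICC factor and would give 1.579. The stated 1.87 is used here.
- N = 2 × (1.96 + 0.842)² × 1.06² × (1 − 0.4²) / 0.315² × 1.87 / 0.70 ≈ 399 per arm, against 400 stated.

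**2. Closed form, with only arm in the imputation model.** Variances are in units of σ²/n, with n the number of parents per arm.
- With complete data: residual 0.97 + school 0.015 × 40 + class 0.015 × 20 = 0.97 + 0.60 + 0.30 = 1.87.
- True variance with fraction f missing: 0.97/(1 − f) + 0.90.
- Within-imputation variance: 1 + 0.87(1 − f)², because two parents keep their correlation only if both are observed. Between-imputation variance: f/(1 − f). Rubin total: 1/(1 − f) + 0.87(1 − f)².

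| f | Rubin | True | SE ratio | Shortfall | Two-sided error, normal |
|---|---|---|---|---|---|
| 5% | 1.838 | 1.921 | 0.978 | 2.2% | 5.5% |
| 10% | 1.816 | 1.978 | 0.958 | 4.2% | 6.0% |
| 20% | 1.807 | 2.113 | 0.925 | 7.5% | 7.0% |
| 30% | 1.855 | 2.286 | 0.901 | 9.9% | 7.7% |

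**3. Simulation.** 20 schools, 2 classes of 20, continuous outcome. Entries are estimated SE divided by true SE. A: 4,000 trials, 20 imputations, pretest correlation 0.5, school-level analysis. B: 2,500 trials, 20 imputations. C: 1,200 trials, 10 imputations. Monte Carlo error of a ratio is about 1/√(2 × trials), that is 1.1%, 1.4% and 2.0%.

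| Imputation model | 5% | 10% | 20% | 30% |
|---|---|---|---|---|
| Arm only (A) | 0.971 | 0.959 | 0.915 | 0.886 |
| Arm + pretest (A) | 0.978 | 0.974 | 0.949 | 0.922 |
| Arm + pretest (B) | – | 0.97 | 0.92-0.93 | 0.89-0.91 |
| Arm + pretest (C) | – | 0.94 | 0.915 | 0.895 |
| School fixed effects + pretest (A) | 1.044 | 1.027 | 1.099 | 1.127 |
| School fixed effects (C) | – | 1.04 | 1.10 | 1.17 |
| Two-level (C) | – | 0.99 | 0.99 | 1.01 |

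Across the closed form and the single-level rows, the shortfall is 2.2% to 6% at 5-10% missing and 5.1% to 11.4% at 20-30% missing. Type I error with t(18) in B was 6.2-6.9% at 20-30% missing. With 1.96 as critical value it was 8.3-8.9%, but part of that comes from ignoring the small number of schools.

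**The case against.** The plan is silent on clustering in the imputation; it does not specify single-level imputation. A reader might infer from the software name that school is excluded, but the text does not say so. MCMC is only an example, and school indicators can be entered in PROC MI. This stands, and the point is therefore conditional on the analysis being run as written.

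A reader might also infer one fixed shortfall, such as 10%. The documents do not support that. In the closed form with arm only, 10% requires about 30% missing, and a pretest in the model reduces the shortfall because it carries part of the school effect. The result also depends on whether the pretest shares the school effect and whether the analysis adjusts for it. Varying both at 20-30% missing gave SE ratios from 0.86 to 0.97 and type I error from 4.1% to 8.2%. The 35% parental refusal in Section 6.2.3 is non-enrolment and cannot serve as the missing fraction.

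Nor is the main result at risk. One sentence in Section 6.8.5 could be read as replacing FIML by imputation, but the next confines PROC MI to sensitivity analyses, and these may never be triggered.

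Finally, a reader might infer that the binary pass indicator is to be imputed under a normal model. Nothing says this. Imputing scores and deriving the pass mark from them is compatible with the text, which simply does not say which is meant.

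What remains is that the plan names its software, type of imputation and combining step but not how clustering enters, and that omitting clustering gives standard errors that are too small.

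**Conclusion.** The point holds as a conditional one about a sensitivity analysis. If PROC MI is run as described, with no school or class term, the combined standard errors are too small by about 2-6% at 5-10% missing and about 5-11% at 20-30% missing. Type I error is then about 6-7% with t(18) at 20-30% missing. The FIML estimate, its standard error and its p-value are unaffected.

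The direction is the same in the closed form and in all three simulations. The size rests on missing fractions that the documents do not give, on the plan's ICCs and on a continuous outcome. The plan combines log-odds, for which the percentages may differ. This is more than a missing detail, because a two-level imputation model kept the ratio at 0.99 to 1.01 in the same setting. That result comes from one simulation with Monte Carlo error of about 2%.

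**What to change.** In Section 6.8.5, for this sensitivity analysis:

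- Use a two-level imputation model with random effects for school and class, including arm, the pretest and the other time points, and list these variables.
- Impute item or total scores and derive the 80% pass mark afterwards. State how this fits with the proration of scales planned in the same section.
- Analyse each completed data set with the same mixed model as the primary analysis, then combine.
- Do not make school fixed effects the lead option. At 20-30% missing they make the standard errors about 10-17% too large, an error of similar size in the other direction, and they omit class, for which Section 6.8.1 posits the larger ICC.

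The cost is a few sentences of text and a little more programming, possibly outside PROC MI, for an analysis that may not be triggered.
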